## 11 Drug Formulation and Procurement

### 11.1 Gilteritinib

Please refer to the current Investigator's Brochure for additional information.

#### 11.1.1 Other Names

██████████

#### 11.1.2 Classification

Gilteritinib is a tyrosine kinase inhibitor under development for the treatment of AML. Gilteritinib has an inhibitory effect on FMS-like tyrosine kinase 3 (FLT3), AXL, leukocyte receptor tyrosine kinase (LTK) and anaplastic lymphoma kinase (ALK).

#### 11.1.3 Storage and Stability

Gilteritinib is an oral drug that is available in a 40 mg tablet. In addition to the active ingredient, gilteritinib 40 mg tablets contain well-characterized excipients. Gilteritinib tablets are round light-yellow, debossed, film-coated tablets. The tablets are contained within a high-density polyethylene bottle. Each bottle of gilteritinib contains 30 tablets.

The storage conditions of gilteritinib tablets 40 mg packed into bottles is 20-25°C (68-77°F) with excursions permitted to 15°C and 30°C (59°F and 86°F). Do not freeze. Protect from light.

#### 11.1.4 Dose Specifics

Gilteritinib 120 mg tablets (three 40 mg tablets) are taken once daily by mouth on days 8-21. Patients will be instructed to take the daily gilteritinib with water as close to the same time each morning as possible. Tablets should not be chewed, crushed or broken.

Gilteritinib will be self-administered at home when patients are not hospitalized, and when scheduled for clinic visits. If a subject forgets to take a dose in the morning and within 6 hours of the planned dosing time, they should be instructed to take their dose. If the subject forgets to take their daily dose and more than 6 hours has passed the planned dosing time, they should be instructed to wait for the next morning to dose. If vomiting occurs after dosing, the subject should not receive another dose, but just wait until the next morning to dose.

Sites should review the medication diary instructions at each visit.

Dose reductions are permitted (Section 6).

#### 11.1.5 Drug Interactions

Treatment with concomitant drugs that are strong inducers of CYP3A and P-gp (e.g., rifampin, phenytoin, St. John's Wort) are prohibited as they can decrease the plasma exposure of gilteritinib. Treatment with concomitant drugs that are strong inhibitors of CYP3A and P-gp (e.g., voriconazole, itraconazole, posaconazole, clarithromycin, erythromycin, captopril, carvedilol, ritonavir, azithromycin) should be avoided with the exception of antibiotics, antifungals and antivirals that are used as standard of care to prevent or treat infections. If CYP3A inhibitors are used concomitantly, patients should be monitored closely for AEs.

Treatment with concomitant drugs that target serotonin 5HT2BR or sigma nonspecific receptor should be avoided with the exception of drugs that are considered absolutely essential for the care of the patient.

Precaution should be used in treatment of gilteritinib with concomitant drugs that are substrates of P-gp (e.g., digoxin, dabigatran etexilate), BCRP (e.g. mitoxantrone, rosuvastatin) and OCT1 (e.g., metformin), since these transporters have been shown to be inhibited by gilteritinib in vitro.

Caution should be used when treating patients concomitantly with gilteritinib and drugs that are known to prolong QT or QTc intervals.

Additionally, patients with moderate or severe hepatic dysfunction as measured by laboratory tests should be closely monitored.

#### 11.1.6 Agent Availability

Gilteritinib will be supplied by Astellas and provided to PrECOG's designated depot. PrECOG designated depot will distribute to sites.

The initial supply of gilteritinib will be sent directly to the site upon site activation. As needed, gilteritinib may be requested by the Principal Investigator (or their authorized designees) at each participating institution. The investigator, or a responsible party designated by the investigator, must maintain a careful record of the receipt, disposition, and return/destruction (site's drug destruction policy must be reviewed and approved by PrECOG before any study drug can be destroyed at a site) of gilteritinib.

#### 11.1.7 Agent Ordering

PrECOG will be responsible for ordering drug for re-supply to the site.

Requests for shipments of gilteritinib to the PrECOG designated depot will be coordinated between PrECOG and Astellas.

#### 11.1.8 Agent Accountability

Gilteritinib will be stored in a secure location. Only authorized pharmacy and study staff will have access to this agent. Drug accountability will be reviewed by PrECOG.

##### 11.1.9.2 QT Prolongation

Arrhythmias due to QT prolongation is a potential risk for gilteritinib. 4.4% of relapse/refractory patients had a maximum post baseline QTcF interval >500 msec and approximately 8.8% of patients had a >60 msec change in their maximum QTc relative to baseline. Although clinically relevant QTc prolongation is not anticipated, additional eligibility criteria

for enrollment (exclusion of patients with QTcF >500 ms, long QT syndrome, hypokalemia or hypomagnesemia) and ECG assessments during induction and consolidation have been implemented.

11.1.9.3 Other Identified Risks

Other identified risks of gilteritinib include peripheral edema, increased blood creatine phosphokinase, myopathy, increased liver transaminase and diarrhea.

11.1.10 Important Potential Risks

11.1.10.1 Cardiac Failure

Cardiac Failure has been reported in oncology clinical studies. Although these patients had other potentially contributing factors including a medical history of cardiac failure, prior chemotherapy treatment (anthracyclines) and concurrent bacteremia/sepsis, the role of gilteritinib could not be completely excluded. Patients should be monitored for signs and symptoms of cardiac failure while being treated with gilteritinib.

11.1.10.2 Pericarditis and Pericardial Effusions

Pericarditis and pericardial effusions has been reported in oncology clinical studies. Some of these patients had concurrent lung infection or sepsis, the role of gilteritinib could not be completely excluded. Patients should be monitored for signs and symptoms of pericarditis and pericardial effusion while being treated with gilteritinib.

11.1.10.3 Pancreatitis Acute

Pancreatitis and pancreatitis acute have been reported in oncology clinical studies. Patients should be monitored for signs and symptoms of pancreatitis and pancreatic acute while being treated with gilteritinib.

11.1.11 Other Potential Risks

Other potential risks of gilteritinib include gastrointestinal obstruction, gastrointestinal perforation, gastrointestinal hemorrhage, differentiation syndrome and squamous cell skin carcinoma.

Please refer to the current Investigator's Brochure for additional information.

11.1.12 Overdose

Neither the effects of overdose of gilteritinib (defined as more than 300 mg for a single dose) nor an antidote to overdose are known. In the case of an overdose, the patient should be closely monitored for adverse reactions and supportive treatment should be administered.

11.2 Midostaurin

Midostaurin will be obtained by the individual study sites as standard of care treatments from commercial stock. Please refer to the commercial package insert for full prescribing information.

11.2.1 Other Names

RYDAPT

11.2.2 Classification

Midostaurin is a kinase inhibitor.

11.2.3 Storage and Stability

Midostaurin is an oral drug that is available in 25 mg capsules.

Store in the original package to protect from moisture at 25°C (77°F); excursions permitted to 15°C to 30°C (59°F to 86°F).

11.2.4 Dose Specifics

Midostaurin 50 mg (two 25 mg capsules) twice a day by mouth on days 8-21. Patients should take their doses at approximately the same time each day, and approximately 12 hours should elapse between the morning and evening doses. Each daily dose should be given with food and a glass of water (~240 mL). Patients should be instructed to swallow capsules whole and not open, break or chew capsules. If vomiting occurs, no re-dosing is allowed prior to the next scheduled dose.

Dose interruptions are permitted (Section 6).

11.2.5 Drug Interactions

Midostaurin is metabolized by CYP3A4 to active compounds. Co-administration of drugs which are potent inducers (e.g., phenytoin) or, especially, potent inhibitors (e.g., itraconazole) of this isoenzyme could decrease or increase midostaurin concentrations, and, potentially, decrease the effectiveness or increase toxicity, respectively.

Potent CYP3A4 inhibitors are thought to represent the most significant potential for drug interactions with midostaurin (Appendix V).

11.2.6 Side Effects

Please refer to the Package Insert.

11.3 Daunorubicin

Daunorubicin will be obtained by the individual study sites as standard of care treatments from commercial stock. Daunorubicin is generic and may be obtained from multiple manufacturers. Please refer to the commercial package insert for full prescribing information.

11.3.1 Other Names

Daunorubicin hydrochloride, Daunomycin, Rubidomycin, Cerubidine

11.3.2 Classification

Anthracycline topoisomerase inhibitor.

11.3.3 Storage and Stability

Store unopened vials in refrigerator, 2° to 8°C (36° to 46°F). Store prepared solution for infusion at room temperature, 15° to 30°C (59° to 86°F) for up to 24 hours. Contains no preservative. Discard unused portion. Protect from light.

11.3.4 Dose Specifics

**Induction:** Daunorubicin 90 mg/m^2/day will be administered IV per package insert or institutional guidelines or over 30-60 minutes Days 1, 2, and 3 (45 mg/m^2/day if receives second cycle of induction).

If patient does not achieve CR or CRi after first cycle of induction, then a second cycle of induction will be given. If second induction is needed, treatment will begin after day 24 for midostaurin (i.e.,  $\geq 3$  days after completing midostaurin) and day 28 for gilteritinib (i.e.,  $\geq 7$  days after completing gilteritinib).

Dose modifications are permitted (Section 6).

#### 11.3.5 Preparation

Daunorubicin is commercially available. Preparation will be per package insert and institutional guidelines.

#### 11.3.6 Drug Interactions

Use of daunorubicin in a patient who has previously received doxorubicin increases the risk of cardiotoxicity. Daunorubicin should not be used in patients who have previously received the recommended maximum cumulative doses of doxorubicin or daunorubicin. Cyclophosphamide used concurrently with daunorubicin may also result in increased cardiotoxicity.

Hepatotoxic medications may impair liver function and increase the risk of toxicity.

Daunorubicin may decrease the effect of ciprofloxacin absorption by altering the intestinal mucosa.

#### 11.3.7 Side Effects

Please refer to Package Insert.

### 11.4 Cytarabine

Cytarabine will be obtained by the individual study sites as standard of care treatments from commercial stock. Cytarabine is generic and may be obtained from multiple manufacturers. Please refer to the commercial package insert for full prescribing information.

#### 11.4.1 Other Names

Cytosar-U, Ara-C, Arabinosyl, cytosine arabinoside

#### 11.4.2 Classification

Antimetabolite.

#### 11.4.3 Storage and Stability

Store at 20°C to 25°C (68°F to 77°F). Protect from light.

The dry powder is stored at room temperature. After reconstitution, cytarabine is stable for 7 days at room temperature and 15 days refrigerated. Solutions with a slight haze should be discarded.

#### 11.4.4 Dose Specifics

**Induction:** Cytarabine 100 mg/m^2/day will be administered by continuous IV infusion for a total of 7 days beginning Day 1.

If patient does not achieve CR or CRi after first cycle of induction, then a second cycle of induction will be given. If second induction is needed, treatment will begin after day 24 for midostaurin (i.e.,  $\geq 3$  days after completing midostaurin) or day 28 for gilteritinib ( $\geq 7$  days after completing gilteritinib).

**Consolidation:** Cytarabine 3 g/m^2\* over approximately 1-3 hours every 12 hours (+/- 2 hour window) on days 1, 3, and 5 or days 1-3 for a total of 6 doses for up to 4 cycles.

\* For patients age  $\geq 55$  or patients with decreased creatinine clearance recommend reducing consolidation cytarabine dose to 1.5 g/m^2.

Dose interruptions are permitted (Section 6).

11.4.5 Preparation

Cytarabine is commercially available. Preparation will be per package insert and institutional guidelines.

11.4.6 Drug Interactions

Reversible decreases in steady-state plasma digoxin concentrations and renal glycoside excretion were observed in patients receiving beta-acetyldigoxin and chemotherapy regimens containing cyclophosphamide, vincristine and prednisone with or without cytarabine injection or procarbazine.

Steady-state plasma digitoxin concentrations did not appear to change. Therefore, monitoring of plasma digoxin levels may be indicated in patients receiving similar combination chemotherapy regimens. The utilization of digitoxin for such patients may be considered as an alternative.

An in vitro interaction study between gentamicin and cytarabine showed a cytarabine related antagonism for the susceptibility of *K. pneumoniae* strains. This study suggests that in patients on cytarabine being treated with gentamicin for a *K. pneumoniae* infection, the lack of a prompt therapeutic response may indicate the need for re-evaluation of antibacterial therapy.

Clinical evidence in one patient showed possible inhibition of fluorocytosine efficacy during therapy with cytarabine injection. This may be due to potential competitive inhibition of its uptake.

11.4.7 Side Effects

Please refer to Package Insert.

## 12 Statistical Considerations

### 12.1 Study Design & Sample Size Considerations

This is a randomized, open-label Phase II study comparing gilteritinib to midostaurin in patients receiving standard induction therapy with cytarabine and daunorubicin in FLT3 mutated AML. Patients will be stratified according to FLT3-TKD vs. FLT3-ITD mutation. Patients with FLT3-ITD mutation will undergo further stratification with NPM1 mutation status (positive vs. negative) and signal ratio (high [ $\geq 0.5$ ] vs. low [ $<0.5$ ] of FLT3 Wild Type). Patients will be randomized to receive standard induction treatment (cytarabine and daunorubicin) with either gilteritinib or midostaurin. If achieving CR or CRi, these patients will go on to receive standard consolidation treatment of high-dose cytarabine with the study drug received during induction (gilteritinib or midostaurin). Patients may proceed to allogeneic transplant after induction or after 0-4 cycles of chemotherapy consolidation. The primary objective of this study is to assess the FLT3 mutation negative CRc (includes CR and CRi) rate of patients who receive gilteritinib compared to those who receive midostaurin in addition to standard therapy with cytarabine and daunorubicin after induction. FLT3 mutation negativity is evaluated by PCR at the end of induction.

Based on a retrospective study performed at John-Hopkins, we assume with the control arm of cytarabine, daunorubicin and midostaurin, the FLT3 mutation negative CRc rate after induction is 40%. With 170 eligible patients with allocation ratio of 1:1 to the two arms, the study will have 80% power to detect an improvement of 20% in the FLT3 mutation negative CRc rate in the gilteritinib arm (i.e., from 40% to 60%) at the one-sided significance level of 0.05 based on Fisher's exact test. Accounting for 5% ineligibility, we will need a total of 179 patients.

Assume 7 FLT3 mutated patients will be accrued each month, the accrual of the study will be completed in 2.1 years.

### 12.2 Statistical Analysis

#### 12.2.1 Primary Objectives

The primary endpoint of this study is the FLT3 mutation negative Composite Complete Response (CRc) [includes CR and CRi] rate. The cut points used for FLT3 mutation negativity are 1% (equivalent to  $10^{-2}$ ) for FLT3-TKD and  $10^{-4}$  for FLT3-ITD (please see Sections 13.1.2.1 and 13.1.2.2 for details). The final analysis of FLT3 mutation negative CRc rate will be performed after the last patient has completed the induction treatment and all patients have MRD response data available. Patients who drop out prior to MRD response assessment or without MRD assessment will be counted as non-responders in the analysis. The FLT3 mutation negative CRc rate will be compared between gilteritinib and midostaurin arms using Fisher's exact test. All eligible and treated patients will be included into the analysis. Two-sided 90% confidence interval on the difference in the FLT3 mutation negative CRc rate will be provided based on the normal approximation to the difference of two independent binomial proportions with continuity correction.

#### 12.2.2 Secondary and Exploratory Objectives

As a secondary objective, the FLT3 mutation negative Complete Response (CR) rate of patients with FLT3 mutated AML who receive gilteritinib will be compared to those who receive midostaurin in addition to standard therapy with cytarabine and daunorubicin after induction. The final analysis of FLT3 mutation negative CR rate will be performed after the last patient has completed the induction treatment and all patients have MRD response data available. Patients who drop out prior to MRD response assessment will be counted as non-responders in the analysis. The FLT3 mutation negative CR rate will be compared between gilteritinib and midostaurin

arms using Fisher's exact test. Two-sided 90% confidence interval on the difference in the FLT3 mutation negative CR rate will be provided based on the normal approximation to the difference of two independent binomial proportions with continuity correction.

The MRD- CRc rate of patients with FLT3 mutated AML who receive gilteritinib will be compared to those who receive midostaurin. MRD will be measured by flow cytometry. The MRD- CRc rate will be compared using Fisher's exact test. Two-sided 90% confidence interval on the difference in the MRD- CRc rate will be provided based on the normal approximation to the difference of two independent binomial proportions with continuity correction.

The CRc (CR or CRi, as defined in Section 9) rate of patients with FLT3 mutated AML who receive gilteritinib will also be compared to those who receive midostaurin. The CRc rate will be compared using Fisher's exact test. Two-sided 90% confidence interval on the difference in the CRc rate will be provided based on the normal approximation to the difference of two independent binomial proportions with continuity correction. One of the secondary objectives of this study is to compare event free survival (EFS) of patients who receive gilteritinib to those who receive midostaurin in addition to cytarabine and daunorubicin after induction and high-dose cytarabine after consolidation. EFS is defined as time from study randomization to the date of induction treatment failure, relapse after CRc or to death from any cause after CRc, whichever comes first. For patients alive without induction treatment failure or relapse after CRc, EFS will be censored at the date of the last disease evaluation. The main analysis of EFS is to set the event date for induction treatment failure on day 1 of randomization.

We assume with the control arm of cytarabine/daunorubicin plus midostaurin, for FLT3 mutated patients, the cure rate of EFS is 25% and the median EFS for the non-cure patients is 6 months. With approximately 170 eligible patients, the study will have 80% power to detect 38% reduction in hazard rate in EFS in the gilteritinib arm, using one-sided log rank test at the significance level of 0.05 and assuming 2 years of follow-up. The number of EFS events needed is about 110.

We will also assess OS of patients who receive gilteritinib to those who receive midostaurin in addition to cytarabine and daunorubicin after induction and high-dose cytarabine after consolidation. OS is defined as the time between randomization and death from any cause. The censored follow-up time for patients without death information is the date of last contact.

The final analysis of EFS and OS will be performed when the full information of EFS is reached (i.e., 110 events have occurred). Estimates of EFS and OS, including medians and confidence intervals, will be calculated using the Kaplan-Meier method. Comparison of EFS and OS between treatment arms will be conducted using the one-sided stratified log-rank test with FLT3 mutation (TKD vs ITD), FLT3-ITD mutation signal ratio (high  $\geq 0.5$  vs. low  $<0.5$  of FLT3 Wild Type), and NPM1 mutation status, the same stratification factors used in randomization. Cox proportional hazards models, stratified on the same factors above, will also be used to assess the treatment effect.

A sensitivity analysis of EFS will be performed where follow-up will be censored at the start of transplantation.

Comparison of CRc rate, EFS and OS between treatment arms will also be conducted in patients with de novo AML, t-AML and AML-MRC separately; and in patients with favorable, intermediate, and adverse risk separately, determined by 2017 ELN risk classification.

To determine the predictive value of Minimal Residual Disease (MRD) positivity and negativity post induction therapy. EFS and OS of the patients who achieved MRD negative after induction will be compared with those who did not. All CRc patients who have MRD response evaluated post induction will be included into this analysis. The interaction of treatment and MRD status will be tested in the Cox regression model. If a strong interaction effect is detected, the treatment effect will be looked at within MRD+ and MRD- patients separately.

The correlation between MRD by molecular studies and morphology will be assessed. McNemar's test will be used to assess the concordance of the measurements.

For patients who are FLT3 mutation positive after induction and administered consolidation, the FLT3 mutation negative CRc rate after first cycle of consolidation and their corresponding 90% confidence intervals will be given by treatment arm.

To assess the correlation of FLT3 mutation with outcome, the EFS and OS of those patients with FLT3-TKD mutation will be compared with patients with FLT3-ITD mutation. Among those patients with FLT3-ITD mutation, EFS and OS will be compared among those with ITD signal ratio >0.5 with those ≤ 0.5 of FLT3 Wild Type.

As per NCI CTCAE Version 5.0, the term toxicity is defined as adverse events that are classified as either possibly, probably, or definitely related to study treatment. The maximum grade for each type of toxicity will be recorded for each patient, and frequency tables will be reviewed to determine toxicity patterns during induction and consolidation separately by treatment arm.

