#### **ARM B (7+3) + Midostaurin**

- **Cytarabine** 100 mg/m^2/day will be administered by continuous IV infusion for a total of 7 days beginning Day 1
- **Daunorubicin** 90 mg/m^2/day will be administered IV per package insert or per institutional guidelines or over 30-60 minutes Days 1,2,3.
- **Midostaurin** 50 mg orally BID x 14 days beginning on day 8

If there is a delay in starting FLT3 inhibitors in Arm A or Arm B (due to obtaining drug, i.e. insurance, formulary, etc.), the FLT3 inhibitor will need to stop after Day 21 dose (i.e., Day 21 or Day 22 [if FLT3 inhibitor started on Day 9]). No missed doses will be made up.

**NOTE:** If second cycle of induction is needed, daunorubicin dose will be decreased to 45 mg/m^2/day IV Days 1,2,3.

---

A bone marrow aspirate/biopsy will be performed on all patients on Day 21 (+/-1 day window; delays due to holidays, weekends, or other unforeseen circumstances will be permitted) to determine the need for a second induction cycle. If the marrow aspirate/biopsy is inadequate to make a determination, consider repeating the bone marrow assessment in 5-7 days.

**Arm A + Gilteritinib:** If second cycle of induction is planned, treatment will begin after Day 28 (i.e.,  $\geq 7$  days after completing gilteritinib) but no later than Day 45.

**Arm B + Midostaurin:** If second cycle of induction is planned, treatment will begin after Day 24 (i.e.,  $\geq 3$  days after completing midostaurin) but no later than Day 45.

A repeat bone marrow aspirate/biopsy should be done to assess for response and MRD status upon peripheral blood count recovery (Absolute Neutrophil Count (ANC)  $\geq 1000/\text{mm}^3$ , platelets  $\geq 100,000/\text{mm}^3$ ) but no later than Day 60 after initiation of the first cycle of induction therapy for patients who receive 1 cycle of induction or no later than Day 60 after initiation of the second cycle of induction therapy (i.e., Day 84-105) for patients who receive 2 cycles of induction (MRD sample will be obtained by Day 60 on all patients even if counts have not recovered. The only exception is a patient who has been declared a relapse based on blood counts).

Patients who do not achieve a CR or CR with incomplete hematologic recovery (CRi) by Day 60 if one cycle and Day 84-105 if 2 cycles of induction therapy will be removed from study.

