### 7.3 Criteria for Removal from Study Treatment

A genuine effort will be made to determine the reason(s) why a patient fails to return for the necessary visits or is discontinued from the trial, should this occur. It will be documented whether or not each patient completed the clinical study. If for any patient study treatment or observations were discontinued, the reason will be recorded on the appropriate electronic case report form. Reasons that a patient may discontinue treatment in a clinical study are considered to constitute one of the following:

1. If the patient has already initiated midostaurin or gilteritinib therapy and CNS involvement is detected, the patient may either come off protocol therapy immediately or complete therapy through Day 21 then will be removed from protocol treatment.
2. Failure to achieve CR or CRi after 2 cycles of induction.

3. Patient requires treatment with therapy not allowed per protocol, or patient goes on to receive HSCT.
4. Recurrence of disease or documented progression of disease.
5. Intercurrent illness that prevents further administration of treatment per investigator discretion.
6. Unacceptable adverse events.
7. Investigator and/or patient discontinue chemotherapy.
8. Pregnancy.
9. Develops a second malignancy (except for non-melanoma skin cancer or cervical carcinoma in-situ) that requires treatment, which would interfere with this study.
10. The patient may choose to withdraw from the study at any time for any reason.
11. General or specific changes in the patient's condition that render the patient unacceptable for further treatment in the judgment of the investigator.
12. Severe non-compliance to protocol as judged by the investigator.
13. Lost to follow-up.
14. Death.
15. Closure of study by PrECOG.

Patients who discontinue study treatment early should be followed for response assessments and survival, if possible. Follow-up will continue per Section 10, as applicable.

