## 9 Measurement of Effect

Response assessments will require a bone marrow aspirate/biopsy to be performed. The 2017 European LeukemiaNet (ELN) recommendations will be used to assess response.

End of Cycle = Count Recovery

A bone marrow aspirate/biopsy is required on all patients on Day 21 (+/- 1 day window; delays due to holidays, weekends, or other unforeseen circumstances will be permitted) after initiating the first cycle of induction. Patients who have residual disease will be eligible to receive a second cycle of induction identical to the first (Section 10).

A repeat bone marrow aspirate/biopsy should be done to assess for response and MRD upon count recovery (Absolute Neutrophil Count (ANC)  $\geq$  1000/mm^3, platelets  $\geq$  100,000/mm^3) but no later than Day 60 after initiation of the cycle of induction therapy (i.e., Day 60 or patients who receive one cycle of induction and Day 84-105 for patients that receive 2 cycles of induction. (MRD sample will be obtained by Day 60 on all patients even if counts have not recovered. The only exception is a patient who has been declared a relapse based on blood counts).

Patients who do not achieve a CR or CRi by Day 60 after initiation of the last cycle of induction therapy will be removed from study.

Patients are not eligible to proceed to Consolidation unless bone marrow samples are obtained for MRD at the time of CR/CRi.

A bone marrow aspirate/biopsy is also required at the end of the first Consolidation cycle to assess disease and MRD status.

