9.6 Treatment Failure

Primary Refractory Disease: No CR or CRi after 2 courses of intensive induction treatment or recovery with blasts/loss of CR/CRi within 28 days of documentation of initial CR/CRi. Exclude patients with death in aplasia or death due to indeterminate cause.

Death in Aplasia: Deaths occurring  $\geq 7$  days following completion of initial treatment while cytopenic; with an aplastic or hypoplastic bone marrow obtained within 7 days of death, without evidence of persistent leukemia.

Death from Indeterminate Cause: Deaths occurring before completion of therapy, or  $<7$  days following its completion; or deaths occurring  $\geq 7$  days following completion of initial therapy with no blasts in the blood, but no bone marrow examination available.

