9.8 Relapse

Relapse following CR/CRi is defined as (only if this happens  $>28$  days after CR/CRi):

Bone marrow blasts  $\geq 5\%$ ; or reappearance of blasts in the blood; or development of extramedullary disease.

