##### **4.4.2. Discontinue Treatment**

Patients who do not achieve a CR or CR with incomplete hematologic recovery (CRi) by Day 60 if one cycle and Day 84-105 if 2 cycles of induction therapy will be removed from study.

Patients who achieve CR or CRi can proceed to post remission consolidation therapy on study or may proceed to allogeneic transplant if desired.

Patients who go to transplant or any other non-protocol leukemia directed therapy will complete an end of treatment visit and will be followed for relapse and survival only.

Reasons that a patient may discontinue treatment in a clinical study are considered to constitute one of the following:

1. Failure to achieve CR or CRi after 1- 2 cycles of induction.
2. Patient requires treatment with therapy not allowed per protocol, or patient goes on to receive HSCT.
3. Recurrence of disease or documented progression of disease.

4. Intercurrent illness that prevents further administration of treatment per investigator discretion.
5. Unacceptable adverse events.
6. Investigator and/or patient discontinue chemotherapy.
7. Pregnancy.
8. Develops a second malignancy (except for non-melanoma skin cancer or cervical carcinoma in-situ) that requires treatment, which would interfere with this study.
9. The patient may choose to withdraw from the study at any time for any reason.
10. General or specific changes in the patient's condition that render the patient unacceptable for further treatment in the judgment of the investigator.
11. Severe non-compliance to protocol as judged by the investigator.
12. Lost to follow-up.
13. Death.
14. Closure of study by PrECOG.

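### Would leaving induction treatment failure undefined cause living one-cycle non-responders to be censored in EFS?

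*Protocol*

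**What the plan says.** Protocol 12.2.2 measures EFS from randomization to the "date of induction treatment failure, relapse after CRc or to death from any cause after CRc, whichever comes first". A patient who is alive with neither induction failure nor relapse is censored at the last disease evaluation. In the main analysis an induction failure is dated to day 1. SAP 5.6 and 7.6.6 repeat this. None of these places says what an induction treatment failure is.

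The related passages are:

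- Protocol 9.6 has three categories of treatment failure. The first reads "Primary Refractory Disease: No CR or CRi after 2 courses of intensive induction treatment". That same category has an alternative limb for early failure, worded as "recovery with blasts/loss of CR/CRi within 28 days of documentation of initial CR/CRi". The other two are deaths: in aplasia, and from indeterminate cause.
- Protocol 9.8 recognises relapse only when it comes more than 28 days after CR/CRi.
- Protocol 5.2.1 says that patients without CR or CRi "by Day 60 if one cycle and Day 84-105 if 2 cycles of induction therapy will be removed from study". Protocol 9 applies the same removal to "Patients who do not achieve a CR or CRi by Day 60 after initiation of the last cycle of induction therapy".
- Protocol 7.3 lists as a reason for stopping treatment "Failure to achieve CR or CRi after 2 cycles of induction". The matching item in SAP 4.4.2 is "Failure to achieve CR or CRi after 1- 2 cycles of induction".

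The EFS event count has two uses: a futility look once more than 55 events have occurred, and the final EFS and OS analyses at 110 (protocol 12.2.2 and 12.3.1; SAP 7.6.7 and 7.7).

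**The concern.** A programmer who searches for a definition finds only 9.6. For a living patient who never remitted, it asks for two courses. The protocol foresees patients who stop after one cycle without remission. Under 9.6 as written such a patient is not a failure, so while alive the patient falls under the censoring sentence and a known non-responder is treated as event-free at last evaluation. If the patient dies with persistent leukaemia seven or more days after therapy, no rule applies: neither death category in 9.6 fits, the death is not after CRc, and the censoring sentence covers only the living.

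At stake would be the secondary EFS comparison in an open-label trial, a futility look at which the study may be ended, and the timing of the final EFS and OS analyses.

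**Working it through.** **1. The plan's own figure.** Inputs from protocol 12.2.2: hazard ratio 1 − 0.38 = 0.62, one-sided 0.05, 80% power. The Schoenfeld formula for equal arms gives 4 × (1.645 + 0.842)² / (ln 0.62)² = 4 × 6.18 / 0.2285 = 108.2, rounded up to 109. Freedman's formula gives 113. The stated figure of about 110 is reproduced.

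The planning curve applies to all 170 patients: control S(t) = 0.25 + 0.75 exp(−t ln 2 / 6), gilteritinib S(t)^0.62, 85 per arm, accrual over 179/7 = 25.6 months and 24 further months of follow-up. It yields 110.2 expected events. The sizing sets aside no class of patients who fail and are not counted.

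**2. The two readings side by side.**

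| Patient | 9.6 taken literally | Structure of the EFS definition |
|---|---|---|
| Alive, no CR/CRi after two cycles | failure | failure |
| Alive, no CR/CRi after one cycle | censored | failure |
| Dies before CRc, in aplasia or of indeterminate cause | failure | failure |
| Dies before CRc with persistent leukaemia, one cycle, 7+ days after therapy | no rule | failure |
| Loses CR/CRi within 28 days | failure | failure, through 9.6 |
| Alive, withdraws before assessment | censored | censored |

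The readings part on rows two and four only. Three things settle those rows:

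- Relapse and death are each limited to patients who reached CRc. The first event is the only one left for patients who did not, so it has to cover all of them.
- Protocol 5.2.1 and 9 give the deadline: Day 60 after the start of the last induction cycle, with one-cycle patients named in 5.2.1. SAP 4.4.2 also names one or two cycles.
- EFS does not cite 9.6. The two-course wording there defines primary refractory disease, one category of three. If its recovery-with-blasts limb stands alone, some one-cycle patients are failures even under 9.6.

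In row five, early loss is already failure under 9.6, so the patient is not lost as an event. Only the date could be debated. If remission is documented by the deadline, the loss comes by Day 60 + 28 = 88 after one cycle, or Day 105 + 28 = 133 after two, counted from the start of induction.

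**3. Size if the literal reading were used.** The documents give no failure rate by arm and no one-cycle share, so both are assumed. With 20% failing and half of them after one cycle, 170 × 0.20 × 0.50 = 17 patients would move from event to censored if none had died and been counted.

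Simulations with no true effect (85 per arm, 20,000 trials per case, unstratified one-sided 0.05 log-rank, 20% failure in each arm) give:

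- one-cycle shares of 50% in both arms: 4.9–5.4% rejection;
- shares of 60% (gilteritinib) against 40%: 9.7–10.1% if no one-cycle failure counts, 6.9–7.2% if half have died and count;
- shares reversed, 40% against 60%: 2.0–4.2%;
- all failures counted: 4.9–5.1%.

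The departure from 5% thus comes from the assumed imbalance. The only arm difference in the documents that bears on it is the earliest start of a second induction, after Day 28 against after Day 24, both with a limit of Day 45.

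**The case for a change.** The strongest contrary case is that intent is not text. The natural reading has to be assembled from sections that EFS does not cite. SAP 4.4.2 is a discontinuation list that differs from protocol 7.3, although SAP 2.1 describes its design material as extracted from the protocol and SAP 8 announces no changes. The trial is open-label, so a reading chosen after outcomes are known could be called post hoc. The event count also has little slack: under the planning curve the expected number of events ever is 85 × 0.75 + 85 × (1 − 0.25^0.62) = 63.8 + 49.0 = 112.8, against a trigger of 110.

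What stands is that the term is undefined and that the one-cycle and two-cycle passages differ. The documents also differ on whether a second cycle may be given (protocol schema and section 10) or will be given (11.3.4 and 11.4.4). Those passages must be reconciled in their own right, but the EFS reading is the same either way.

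The rest carries less weight. The narrow margin at 110 belongs to the planning assumptions and is not caused by this wording; with the hazard ratio acting on non-cured patients only, the expected maximum is 2 × 85 × 0.75 = 127.5. Patients who withdraw alive before assessment do have a rule, the censoring sentence. That it differs from the non-responder rule for the primary endpoint is not an error. The EFS futility look comes no earlier than the final CRc analysis, after the last patient has completed induction, so it cannot cut accrual short. It is also permissive, and requires a lower 90% bound for the hazard ratio above 1.

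**Conclusion.** The concern does not hold as a fault in the analysis. A definition is missing, but the EFS wording together with the end-of-induction deadline leads an analyst to the sound result: every patient without CR/CRi by that deadline, including one who dies before CRc, is a day-1 failure whatever the number of cycles. On that reading the event target is unchanged and simulated rejection is 4.9–5.1%.

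Harm needs two things at once: use of a definition that EFS does not cite, and one-cycle shares that differ by arm. The documents support neither, so no effect on the error rate or on the event triggers can be claimed for this trial. EFS is a secondary endpoint of a Phase II study, and the primary endpoint and the OS definition are unaffected. A sentence recording the reading would do no harm, but it would not alter what is analysed.

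This conclusion assumes that analysts take the three EFS events as covering all patients. The separate table templates named in the SAP may already state the derivation, but they were not available, and nothing here relies on them.
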